5. STUDY PROCEDURES

5.1 Screening visit

- Subjects who meet the inclusion/exclusion criteria will be enrolled, and written informed consent will be obtained.
- The subject's demographic data, medical history, duration and onset of AGA, and current usage of any topical or systemic drug for the treatment of AGA will be recorded.

5.2 Treatment Visit

- In addition to oral explanations, participants will be given written instructions on how to use solutions and storage conditions.
- Subjects will not be permitted to apply their usual hair cosmetics products and will be requested not to alter their usual routine hair care during the study period.
- Subjects will be instructed to avoid the use of any prescribed and/or nonprescription therapeutic agents for preventing hair loss or hair growth during the study period.
- Baseline hair thickness will be taken, and every three months, it will be repeated. For reproducibility, the target location on the scalp, where the hair thickness will be measured over time, consist of Intersecting three distances from the fixed anatomical locations.

Treatment randomization

Before the study begins, a random number table will be generated (in 1:1 ratio) for each study participant according to the subject number. The number will indicate whether treatment or control will be taken on the study groups. “0” represents a 5% minoxidil topical solution whereas “1” represents a 5% minoxidil topical solution plus the topical herbal solution.

Blinding

Dermatologist and the randomized subjects will be blinded to the subject’s allocation. It is necessary to use blinded treatment in order to reduce potential bias during data collection and evaluation of study outcomes.

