2. STUDY DESIGN

This study will be done on male patients with androgenic hair loss. The patients will be selected by volunteers attending the Dermatology department of Sina Hospital and eligible individuals will be selected among them. The participants will be randomly allocated (using random number tables) to two groups; the first group will receive a 5% minoxidil topical solution, and the second group will receive a 5% minoxidil topical solution plus the topical herbal solution for 36 weeks. The hair thickness will be measured to determine efficacy at baseline, 12, 24, and 36 weeks. The patient's questionnaire self-evaluation and side effects will also be evaluated.

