5.3 Follow-up visits

- **3 and 6-month follow-up visit**
 - Hair thickness will be measured via a digital micrometer.
 - At each follow-up visit, adverse events will be recorded.
- **9-month follow-up visit**
 - Hair thickness will be measured via a digital micrometer.
 - Adverse events will be recorded.
 - Subjects will complete a self-assessment questionnaire.

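### Subjects are said to be blinded, but one arm gets minoxidil alone and the other minoxidil plus a herbal solution; unless an undescribed matched presentation exists, the arms do not deliver that blind, and the self-rated secondary results are exposed.

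*Combined protocol and SAP*

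**What the plan says.** All references are to the combined protocol and SAP.

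- **Blinding (Section 5.2).** "Dermatologist and the randomized subjects will be blinded". The reason follows: "It is necessary to use blinded treatment in order to reduce potential bias during data collection and evaluation of study outcomes". No method is given.
- **Arms (Section 2).** The control arm is defined thus: "the first group will receive a 5% minoxidil topical solution". For the test arm, the same section reads: "the second group will receive a 5% minoxidil topical solution plus the topical herbal solution for 36 weeks". The randomization paragraph of Section 5.2 repeats this: code 1 "represents a 5% minoxidil topical solution plus the topical herbal solution", and code 0 is the minoxidil solution.
- **Instructions (Section 5.2).** "participants will be given written instructions on how to use solutions and storage conditions". The sentence does not distinguish the arms.
- **Primary outcome (Sections 2 and 6.1).** "The hair thickness will be measured to determine efficacy at baseline, 12, 24, and 36 weeks". Section 6.1 has a blinded investigator take the readings with a digital micrometer.
- **Self-assessment (Sections 5.3, 6.2, 9 and 11).** At the 9-month visit, "Subjects will complete a self-assessment questionnaire". It covers improvement and satisfaction. Section 9 bases efficacy on the secondary as well as the primary measures, and Section 11 compares the questionnaire by Mann-Whitney.
- **Adverse events (Sections 5.3, 6.2 and 10).** They are recorded at each follow-up visit. The reactions Section 10 expects include scalp itching and headache.

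**The concern.** In an add-on design, a subject blind does not follow from the arm definitions. If one group applies a product and the other applies that product and something more, subjects can be kept unaware only by a specific device: a dummy, a premixed preparation, or products matched in appearance, odour and packaging. The plan asserts the blind and names no device.

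The questionnaire is where this matters most, because the subject is the rater and the item rated is an opinion about the result. Section 3 already puts the view that herbal remedies are marked by patient satisfaction and fewer side effects. If subjects share that view and know they have the herbal product, a better score could reflect the product, the expectation, or both. The Mann-Whitney test compares the two sets of scores whatever their cause and cannot separate these. Reports of itching or headache could move for the same reason. A publication that called the trial subject-blinded would then present these comparisons as stronger than they are.

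**Working it through.** The plan has no figure to reproduce. The check is a reading of the sections side by side.

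**Step 1. Is a masking device described?** The available text was searched for a placebo or vehicle, a single combined preparation, matched colour or odour, identical containers, coded supply, and common instructions for the two arms.

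| Section | What it gives | Masking device? |
|---|---|---|
| 2, Study Design | The two arm definitions | None |
| 5.2, instructions | Written instructions on solutions | None; same content for both arms not stated |
| 5.2, randomization | Codes 0 and 1, at 1:1 | None |
| 5.2, Blinding | Who is blinded, and why | None |
| 7, Study Equipment | Micrometer and pH meter | None |

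**Step 2. What follows from the arms?** There are two cases.

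- *The presentations are indistinguishable but not described.* The blinding statement is then true and only the description is missing. The word joining the two solutions in Sections 2 and 5.2 does not say whether there is one container or two, so this case is open.
- *The arms are supplied as the text reads.* One group has minoxidil and the other has minoxidil and a further solution. A subject who knows what the two arms are can infer his own. Section 4.4 has an investigator explain the protocol verbally to interested clinic patients. Whether that covers the arms is not stated.

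The text does not decide between the cases. The blind is therefore claimed but not secured.

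**Step 3. Which outcomes depend on the subject blind?**

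| Outcome | Who rates it | If subjects know their arm |
|---|---|---|
| Hair thickness (6.1), primary | Blinded investigator with an instrument | Largely protected; remaining routes are a subject who discloses his products or uses them differently |
| Questionnaire (5.3, 6.2), secondary | The subject | Directly exposed |
| Adverse events (5.3, 6.2), secondary | Recorder and method of elicitation not stated | Symptoms such as itching and headache exposed through the subject's report |

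**Step 4. Can the bias be sized?** No. That would need the questionnaire scale, its spread, the number of subjects per arm and an expectation shift. The documents give none of these, so any figure would only restate assumptions.

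**The case against.** The strongest reply is that this is an omitted description and not a design fault. The plan says subjects are blinded, so on its face the rater of the questionnaire is blinded. It says that blinded treatment is needed, and it gives instructions on solutions without splitting them by arm, which would fit a matched presentation. The consent form, where subjects would ordinarily learn what they will apply, was not available for this review, so nothing can be inferred from its absence. The primary outcome is an instrument reading by a blinded investigator.

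Much of this stands. A matched or premixed product is not excluded, so the conclusion must be conditional. The protection of the primary outcome is real. What does not stand is the inference that the existing sentences settle the matter. One states an aim. The other uses a plural that suits a single sheet covering different products just as well. Section 5.2 makes the claim and is where the method belongs.

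A reader might infer three stronger things, and the documents support none of them:

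- **That the blind fails, or that the trial is in effect open-label.** The form in which the products are supplied is not described, so failure is not shown.
- **That the primary result is biased.** Section 6.1 names a blinded assessor with an instrument; only indirect routes remain.
- **That the questionnaire result is inflated by some stated amount.** No input for such a figure exists in the plan.

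**Conclusion.** The point holds in conditional form and should be fixed. As written, the arms do not deliver the subject blind that Section 5.2 claims. If no undescribed matched presentation exists, the 9-month questionnaire and subject-reported symptoms are open to expectation bias, and a difference between arms on them could not be attributed to the herbal solution alone. The direct exposure is confined to secondary outcomes, and its size cannot be estimated from the documents.

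This rests on two assumptions: that the parts not available for review, the consent form in particular, do not describe a masking device; and that subjects know what the two arms are. If either is wrong, the risk to these outcomes shrinks or disappears, but Section 5.2 would still not let a reader verify the blind.

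**What to change.** 1. **In any case, in Section 5.2:** instruct subjects not to reveal which products they use to the investigator who measures hair thickness. This closes the disclosure route to the primary outcome.
2. **Unless the sponsor confirms that presentations are indistinguishable across arms, and states how:** remove the randomized subjects from the blinding sentence of Section 5.2, describe the trial as assessor-blinded, and add to Section 9 words such as: *The questionnaire and symptom-type adverse events come from subjects who were not blinded, and are interpreted with that limitation.*

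If the presentations are already indistinguishable, stating the number of containers, appearance, odour and instructions in each arm takes one or two sentences, and the claim of subject blinding can stay.

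**Cost.** A few sentences and a weaker claim for the questionnaire. Section 13.3 requires all changes to go to the ethics committee. Its wording is garbled but, read naturally, it also asks for approval before a change that affects safety or the validity of the study is put in place, and withdrawing a stated blind plausibly falls there. The primary comparison is unchanged.

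Newly adding a vehicle to the control arm is a different matter. It needs an extra preparation and changes the comparator from the 5% minoxidil named in Section 1 to minoxidil plus vehicle, for the primary outcome too. This point does not require it.

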5.3 Follow-up visits

- **3 and 6-month follow-up visit**
 - Hair thickness will be measured via a digital micrometer.
 - At each follow-up visit, adverse events will be recorded.
- **9-month follow-up visit**
 - Hair thickness will be measured via a digital micrometer.
 - Adverse events will be recorded.
 - Subjects will complete a self-assessment questionnaire.

6. DATA COLLECTION AND REPORTING

6.1 Primary Outcome Measures

Hair thickness via a digital micrometer will record for each subject by a blinded investigator at the treatment visit (before treatment) and during the three months, six months, and 9-month follow-up visits.

6.2 Secondary Outcome Measures

1. Patients self - assessment questionnaire of improvement and overall satisfaction scores will be performed at the 9-month follow-up visit (the end of the study).
2. At each follow-up visits, adverse events will be recorded

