4.2 Exclusion criteria

- Used any of topical product in the target region interfering with the study product in the last 12 months
- Within the past six months receiving of chemotherapy/cytotoxic agents
- Clinical diagnosis of alopecia areata or other non-AGA forms of alopecia

- Uncontrolled hypertension
- Any dermatological disorders in the scalp, such as fungal or bacterial infections, eczema, atopic dermatitis, seborrheic dermatitis, psoriasis, sun damage, skin cancer
- Hormonal diseases, such as thyroid disorders and diabetes.
- Smokers
- Liver and kidney disease
- History of hair transplants
- History of surgical correction of hair loss on the scalp
- Subject having dyed, bleached hair, or with a permanent wave before study start.
- No written consent

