10. SAFETY ASSESSMENT

Any procedure has potential risks. According to the herbal origin, the topical herbal solution does not hold any chance of dangerous reactions or systematic disease. The threat from the use of topical solutions may include scalp itching, scalp dryness, and headache. The procedures used in this study may cause all, some, or none of the risks and side effects listed. Each study participant will be informed about the occurrence of these adverse events, and phone numbers will be given for answering any questions. Telephone contact with the investigator will be available 24 hours per day, seven days per week. Treatment for adverse events will be per standard of care from a dermatologist in the Department of Dermatology.

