11. STATISTICAL ANALYSIS PLAN (SAP)

The statistical analysis will be performed using SPSS software 25 (SPSS Inc., Chicago, IL, USA). The normalcy of continuous data will be checked using the Kolmogorov-Smirnov Test. Mean (SD) will be calculated for all normally distributed continuous variables, e.g., age, duration of disease, hair diameter, etc. The unpaired (independent) t-test and paired t-test will be applied to compare the mean of hair diameter between two study groups and within

groups, respectively. For differences between self-assessment questionnaires, the Mann-Whitney test will be performed. At or before the time of the Week 0 administration, subject demographics, hair diameter, and duration of AGA will be summarized. All statistical tests will be two-side and will perform at a significance level of p -value < 0.05 .

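### Adverse events are a secondary outcome, but the three expected reactions are not checked at baseline, so existing complaints may be counted and would dilute a difference between arms

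*Combined protocol and SAP*

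**What the plan says.** Section 6.2 lists adverse events as the second secondary outcome: "At each follow-up visits, adverse events will be recorded". Section 5.3 gives the schedule. For months 3 and 6 it says "At each follow-up visit, adverse events will be recorded", and it repeats the instruction for month 9. No adverse-event or symptom entry comes before treatment.

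Section 10 names the reactions to be expected: "The threat from the use of topical solutions may include scalp itching, scalp dryness, and headache".

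The baseline steps are these:
- Screening (section 5.1) collects demographic data and then "medical history, duration and onset of AGA, and current usage of any topical or systemic drug for the treatment of AGA will be recorded".
- The treatment visit (section 5.2) adds one measurement: "Baseline hair thickness will be taken, and every three months, it will be repeated".
- The SAP (section 11) limits the baseline summary in the same way: "At or before the time of the Week 0 administration, subject demographics, hair diameter, and duration of AGA will be summarized".

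On the other side, section 4.2 excludes "Any dermatological disorders in the scalp, such as fungal or bacterial infections, eczema, atopic dermatitis, seborrheic dermatitis, psoriasis" and further scalp conditions, and section 4.1 requires normal general health.

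The SAP names t-tests for hair diameter and the Mann-Whitney test for the questionnaires. It names no test, table or counting rule for adverse events.

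**The concern.** The primary outcome is measured before treatment (section 6.1), so each man's change can be judged against his own starting point. The adverse-event outcome has no such starting point. Recording is first scheduled three months after treatment begins. A man who then reports itching or headache can be classified as new, worse or unchanged only from memory or from an unstructured history.

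This matters because tolerability is part of the case for the product. Section 3 presents herbal remedies as having fewer side effects, and section 2 says side effects will be evaluated. The control arm receives minoxidil and the other arm receives minoxidil plus the herbal solution, so the safety question is whether the addition brings more reactions. Counting complaints that were already there adds the same background to both arms and makes a true excess look smaller. For an add-on, that error leans towards reassurance. A baseline record that was never taken cannot be recovered later.

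**Working it through.** **No figure to reproduce.** The documents give no sample size, power, adverse-event rate or symptom prevalence. All rates below are assumptions, chosen to show the mechanism and its range.

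**Step 1: the text.** The three reactions in section 10 were compared with each baseline step.

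| Baseline step | Collected | Itching, dryness or headache asked? |
|---|---|---|
| Screening, 5.1 | Demographics, medical history, duration and onset of alopecia, drugs for it | Not named; a history might pick up recurrent headache |
| Treatment visit, 5.2 | Hair thickness | No |
| SAP baseline summary, 11 | Demographics, hair diameter, duration of alopecia | No |

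**Step 2: a model of dilution.**
- From the documents: 1:1 random allocation (section 5.2) and two-sided 0.05 (section 11).
- Assumed: new-onset rates p1 = 10% (control) and p2 = 20% (add-on); a share b of men in each arm has a symptom before treatment; each of these men reports it at follow-up and is counted. This is the worst case for a given b.

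Observed rate in an arm: q = b + (1 − b)p. 
Observed difference: q2 − q1 = (1 − b)(p2 − p1). 
Observed risk ratio: q2 / q1.

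Worked case, b = 5%: q1 = 0.05 + 0.95 × 0.10 = 0.145 and q2 = 0.05 + 0.95 × 0.20 = 0.240. The difference is 9.5 points and the ratio is 0.240 / 0.145 = 1.66.

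**Step 3: what the loss means in numbers of men.** With 80% power (assumed) and average rate q̄ = (q1 + q2)/2,

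n per arm = [1.960 √(2q̄(1 − q̄)) + 0.842 √(q1(1 − q1) + q2(1 − q2))]² / (q2 − q1)².

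| Existing symptoms b | q1 | q2 | Difference (points) | Risk ratio | n per arm |
|---|---|---|---|---|---|
| 0 (existing symptoms separated out) | 10.0% | 20.0% | 10.0 | 2.00 | 199 |
| 5% | 14.5% | 24.0% | 9.5 | 1.66 | 270 |
| 10% | 19.0% | 28.0% | 9.0 | 1.47 | 348 |
| 20% | 28.0% | 36.0% | 8.0 | 1.29 | 533 |

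The n column only expresses the loss of information. The trial is not sized on adverse events, and no such test is planned.

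**Step 4: the case of no true difference.** If p1 = p2, then q1 = q2 for every b, so the expected observed difference is zero. Existing complaints shared equally by randomisation do not create an excess on average; they hide one.

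**Step 5: how far the fix restores the top row.** The 199 assumes that men with existing symptoms worsen at the same rates as others develop symptoms. If instead they can contribute no event, the ratio among the remaining men is still 2.00, but 199 such men per arm are needed: 199 / 0.95 = 210 in all at b = 5%, against 270 without the check, and 199 / 0.80 = 249 at b = 20%, against 533.

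**The case against.** The best defence is that the protocol already keeps the background low. Section 4.2 removes scalp infection, eczema, dermatitis and psoriasis, together with recent interfering topical products and dyed or bleached hair. Section 4.1 asks for normal general health, and the history in section 5.1 could reveal recurrent headache. In ordinary usage an unchanged complaint from before treatment is not an adverse event, so a careful investigator would leave it out. The SAP plans no adverse-event test that could be distorted. At b = 5% a 10-point difference shrinks only to 9.5.

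Much of this stands. It makes large values of b unlikely for itching and dryness, and it limits the harm to a descriptive comparison. It does not close the gap. Itching or dryness without a diagnosed disorder is not excluded, and no exclusion names headache. Nothing requires the history to ask about the three symptoms or to grade them. The small change in the difference at b = 5% also goes with a fall in the risk ratio from 2.00 to 1.66.

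A further objection is that headache, the symptom least covered by the exclusions, is episodic, so asking about it on one day classifies it poorly. That is fair. It is why the baseline question needs a recall period, and even then the classification will be imperfect.

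A reader might go further and infer that the plan counts existing complaints as adverse events, so that rates are overstated in both arms. The documents do not say so; they give no counting rule. Nor do they give any background frequency for these symptoms, so a claim that they are common in untreated men has no support here.

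**Conclusion.** The point holds as a modest gap in data collection. Followed as written, the plan leaves no systematic baseline record of the three reactions it expects, so existing complaints may be counted and cannot be reliably told from new or worsened ones.

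A reader might take this as bias in the safety comparison. The documents do not support that: with 1:1 randomisation the expected effect is dilution of a true difference plus noise, although chance imbalance in a single trial remains possible and, without a baseline record, would go unseen.

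The size depends wholly on assumed rates. At 10% against 20% new onset, with existing symptoms in 5% to 20% of men all counted, the observed risk ratio falls from 2.00 to between 1.66 and 1.29. The scalp exclusions make the lower part of that range more plausible for itching and dryness; headache is less protected. The hair-diameter and questionnaire analyses are not affected. This is a cheap improvement to a listed secondary outcome, not a threat to the trial's main conclusion.

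**What to change.** In section 5.2, before the first application, record the presence and severity of scalp itching, scalp dryness and headache over a stated recent recall period. Use the same wording and severity scale at the 3, 6 and 9-month visits in section 5.3.

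In sections 6.2 and 11, state that events new or worse than baseline will be tabulated by arm, alongside the raw counts. Add the baseline frequency of the three symptoms to the Week 0 summary, so that any chance imbalance can be seen.

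The cost is three extra questions at a visit that already takes place, repeated at follow-up, and a short addition to the SAP. Counts of new or worsened events may be lower than raw counts, which is why both should be shown. One-time recall will still misclassify some episodic headaches.
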